#### 3.6.2 Secondary Outcomes

- Difference in visual analog scale pain (1-10) from prior to procedure to first pain assessment after 60 minutes from completion of ESPB assessed by bedside nurse
  - Historic data from the U-M ED suggests that the median maximal pain reduction (last pain score minus first) in the ED is a mean reduction of 3.4 points (SD = 3.0) from a starting value of 7.9.
- ED operational quality metrics:
  - o Rate of admission to hospital
  - Rate of 72-hour return to the ED
  - ED length of stay
- Safety outcomes and complications at day 30

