#### 4.2 Inclusion Criteria

- Adult (>18 years) emergency department patient presenting with pain due to uncomplicated urolithiasis
- Imaging confirmation of urolithiasis on the index encounter or prior encounter within 7 days
- Patient received one dose of parenteral pain medication in the ED

Rationale for inclusion criteria: We seek to enroll adult patients who have pain that initially required parenteral medications to treat and thus, may benefit from adjunct therapy to treat severe kidney stone related pain.

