# 4.4 Selection of external control patients

External control patients will be selected from a population of patients meeting the following criteria: 1) adult ED patient with the diagnosis of uncomplicated kidney stones; 2) received at least one dose of parenteral medication while in the ED; 3) presentation to the ED between 7/1/2021 and the study start date. From this population, propensity score matched control patients will be selected at a ratio of 3 controls to 1 ESPB patient. External control population patients are not active patients in this study and analysis of their data will be secondary use of data collected during routine care. To provide valid comparison between control patients and ESPB patients, we will compare pain scores obtained by the treatment team (bedside nurse). For all other primary and secondary outcomes, data collection utilizes EHR query that does not require prospective data collection. Please see the data collection section of this protocol for further details.

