# 4.6 Screening

- Study team members will screen for patients using the ED track board and other patient lists/reports within MiChart (EPIC EHR)
- Study team members will review potential subjects' presenting symptoms, prior medical history, and imaging findings
- Study team members will then notify a physician investigator on call of potential subjects currently in the ED
- Physician investigator will review inclusion and exclusion criteria with other study team members (if they did not perform screening personally) as well as the potential subject

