# 5.2 Pre-procedure preparation and safety screen

The proceduralist will explain the ESPB to the patient and answer all questions while obtaining informed consent. After this, the proceduralist and assistants will obtain all nerve block supplies, a department ultrasound system, and properly position the patient. The proceduralist will also ensure that appropriate monitoring equipment (telemetry and pulse oximetry) is in place, primary provider team and primary beside nurse are informed of the procedure, and local anesthetic is obtained from the ED pharmacy. The proceduralist will calculate the maximum safe dose of local anesthetic for the patient. The long-acting local anesthetic to be used in this study is 0.5% Ropivacaine (5 mg/mL) for which the maximum safe dose is 3 mg/kg in 8 hours. The dose will be calculated based on patient weight with a maximum dose of 150 mg (30 mL). Peripheral nerve block is considered on-label use of ropivacaine and the study dose (up to 150 mg) and volume (30 mL) are within the suggested ranges of the approved label. The proceduralist will also confirm the patient does not have allergy to local anesthetic. The proceduralist will also ensure availability of lipid emulsion (Intralipid) in the ED pharmacy. Intralipid is a medication used to treat local anesthetic systemic toxicity (LAST) and would only

be administered in the event of development of LAST. A study team member other than the proceduralist (coordinator or other investigator) will perform a pre-procedure assessment of pain using the visual analog scale. All pre-procedure preparation elements, assessment of pain, and re-confirmation of eligibility criteria will be recorded as the safety screen checklist in the REDCap database.

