# 6.4 Secondary data collection from the EHR

Variables regarding patient demographics, ED operations metrics, diagnoses, medical history, procedures performed, other healthcare encounters, nurse assessments of pain, medications administered, and prescriptions provided during the index ED visit will be obtained using direct query to the EHR databases (RDW, HSDW, Caboodle, Clarity) and confirmed with manual chart review if needed. Using the same EHR query we will also collect data regarding historical control patients (external controls that did not receive ESPB). Control patient data will be collected as secondary data collection of routinely collected health information.

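### Controls may be selected on a visit diagnosis made after the index point while ESPB patients are judged before the block, which would bias the admission comparison against ESPB

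*Combined protocol and SAP*

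**What the plan says.** **ESPB arm.** Section 4.2 enrolls an adult "emergency department patient presenting with pain due to uncomplicated urolithiasis", with imaging confirmation and one parenteral dose already given. Section 4.6 has this judged live: "Study team members will review potential subjects' presenting symptoms, prior medical history, and imaging findings", and then "Study team members will then notify a physician investigator on call of potential subjects currently in the ED". The last check stated is before the block, where under 5.2 the "re-confirmation of eligibility criteria will be recorded as the safety screen checklist in the REDCap database". No section removes a patient from the analysis if the stone proves complicated after that.

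**Control arm.** Section 4.4 draws the pool retrospectively. A control is an "adult ED patient with the diagnosis of uncomplicated kidney stones" who received at least one parenteral dose in the ED during a stated date range. Section 6.4 obtains index-visit variables, diagnoses among them, by EHR query, with manual chart review only where needed, and uses the same query for controls.

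**Not stated.** The protocol does not say what counts as uncomplicated, which codes are used, or whether the control diagnosis is the presenting, ED-discharge or hospital-discharge one. Section 4.1 refers to appendix Figure 1A for the target population, but that figure is not visible in the text available.

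**Outcomes affected.** Section 3.6.2 lists "Rate of admission to hospital" among the ED operational metrics, with 72-hour return and length of stay. Section 7.4 compares these metrics with the external controls.

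**The concern.** The two arms are given the same label by different routes and possibly at different times. A judgement made before the block can use only what is known by then. A recorded visit diagnosis can reflect everything that happened in the visit, including an infection or an intervention that came to light later. If controls are filtered on the second kind of information and ESPB patients on the first, one arm is selected on events after time zero and the other is not.

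This matters because the filter is tied to an outcome under comparison: Section 3.1 itself says that complications of stones can lead to admission. It is also separate from whether the Section 4.3 exclusions are applied to controls. Copying every one of those criteria into 4.4 would still leave this gap if 'uncomplicated' is read from a final diagnosis.

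**Working it through.** **1. Does any passage align the arms?** Three places could do so.
- Section 4.4 could tie the control diagnosis to a time point. It does not.
- Section 7.4 could apply the control rule to ESPB patients. It does not.
- Section 7.2 could match on complication status. Its variables are age, gender, triage acuity, first nursing pain score, Charlson index, and chronic and initial pain medication type. None measures infection, obstruction or renal function, and matching cannot bring back patients who never entered the pool.

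**2. Inputs for size.** The plan has no figure to reproduce here: it gives no admission rate and no rate of turning complicated.
- From the documents: 60 ESPB patients and up to 180 controls (2.10); alpha 0.05, chi-squared or Fisher's exact test (7.1).
- Assumed: c, the share who turn complicated after the index point, 3–10%; a, admission among those, 60–90%; admission otherwise, 10%.
- Also assumed: no true block effect, full removal of such patients from controls, and none removed from ESPB.

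**3. Spurious admission difference.** Control rate = 0.10. ESPB rate = 0.10 × (1 − c) + a × c.
- Low end (c = 0.03, a = 0.60): 0.097 + 0.018 = 0.115, a difference of 1.5 points.
- Midpoints (c = 0.065, a = 0.75): 0.0935 + 0.0488 = 0.142, a difference of 4.2 points.
- High end (c = 0.10, a = 0.90): 0.090 + 0.090 = 0.180, a difference of 8 points.

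**4. Chance of a false result against ESPB.** This is an exact enumeration over both binomials, 60 v 180, treated as independent, counting tables with p<0.05 and higher admission with ESPB.

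| ESPB v control | Uncorrected chi-square | With continuity correction |
|---|---|---|
| 10% v 10% | 3.3% | 1.7% |
| 11.5% v 10% | 6.7% | 3.7% |
| 14.2% v 10% | 17% | 11% |
| 18% v 10% | 39% | 31% |

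**5. Primary outcome.** Section 2.10 reports 572/1071 = 53.4% without a second parenteral dose, so 46.6% with one. Take 46.6% for patients who stay uncomplicated, and let s be the second-dose rate among those who turn complicated, assumed 25–90%. The shift is c × (s − 0.466).
- c = 5%: 0.05 × (0.25 − 0.466) = −1.1 points, to 0.05 × (0.90 − 0.466) = +2.2 points.
- c = 10%: −2.2 to +4.3 points.

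The sign depends on s, about which the documents say nothing.

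**The case against.** The strongest reply is that the key step is not in the text. Section 4.4 does not say that the diagnosis is a final one, or that admission or a later complication removes a control. Section 7.4 compares admission with these controls, so the protocol evidently expects some of them to have been admitted. Section 6.4 allows chart review, which could fix status at an early time. Figure 1A may hold a definition that cannot be seen here. A reader might infer that later-complicated controls certainly leave the pool; the documents do not support that, and the point stands only conditionally.

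Second, ESPB eligibility is checked fairly late. Imaging and a first parenteral dose come first, active treatment for urinary infection is an exclusion (4.3), and eligibility is confirmed again before the block. Complications evident by then can be screened out, so only those that emerge afterwards matter. This argues for a small c, but does not make it zero.

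Third, the consequence is limited. The outcome with a clear direction is secondary, and the bias runs against ESPB, so through admission it would not create a false claim of benefit.

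What remains is that nothing prevents the query from being run on the recorded visit diagnosis, and that this would filter one arm only.

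**Conclusion.** The concern holds in conditional form. The arms are defined differently, no rule aligns them, and matching cannot correct it. If the control diagnosis is the recorded visit diagnosis, the admission comparison is biased against ESPB. Length of stay would probably move the same way, though the documents provide no figures for it.

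The size cannot be computed from the documents. The range of 1.5 to 8 points, and of about 7% to 39% for a false adverse result on the uncorrected test, rests wholly on the assumed inputs and on complete removal from one arm only. The 39% needs both rates at their maximum and should not be quoted alone; the midpoints give about 17%.

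A reader might also infer that every outcome, including second parenteral doses, is tilted against ESPB. That is not supported: the shift in the primary outcome can go either way.

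This should be settled before the control query is run, but it does not invalidate the primary analysis.

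**What to change.** In Section 4.4:
1. Draw the control pool from any ED stone diagnosis or imaging-confirmed stone, without a filter on the final diagnosis.
2. Define 'uncomplicated' once and apply it to both arms, using only facts timestamped before a common index point, for example the later of the first parenteral dose and imaging. Vital signs, urinalysis, imaging reports and antibiotic orders are candidate sources.
3. Keep patients who become complicated after the index point in both arms.

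In Section 7.4, add a sensitivity analysis that applies the visit-diagnosis filter to both arms, and report how many patients it removes from each.

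The cost is a more complex EHR query and some chart confirmation for controls, which 6.4 already allows. ESPB procedures do not change. One limit remains: ESPB patients are checked again just before the block, and controls have no such moment. The time from index point to block should therefore be reported.

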# 2.10 Sample Size

- This study is a two-stage trial with one planned interim analysis for futility
- Based on the prior 30-month time period (as of May 2022), 572 out of 1071 patients (53.4%) presenting to the ED and meeting the inclusion criteria did not require a 2nd parenteral pain medication during the ED encounter. Thus, we estimate a baseline response rate of 55%.
- Prior work by Nobel et al.¹and Aydin et al.² suggests that no patient will require a second dose of any pain medication after ESPB, but we estimate a conservative response rate of 75% for treatment with ESPB.
- Using Simon's optimal two-stage design with these parameters and  $\alpha$  = 0.05,  $\beta$  = 0.10, we estimate that 18 subjects will be required at the interim analysis and 54 subjects will be required to complete this study.
- Using a Bayesian two-stage design, where interim analysis is planned at one-third total enrollment and a stopping rule if there is only a 10% probability of ESPB demonstrating a 75% response rate, we estimate that 45 total subjects (15 at interim analysis) will be required to achieve a 1.4% chance of stopping early and 95.2% chance of rejecting the null hypothesis.
- This study will aim to achieve a total enrollment of 60 subjects who receive ESPB to account for losses to follow up and withdrawals from the study. Up to 180 (3:1 ratio) historical controls will also be included in the study thus the total enrollment including both treatment and control patients is 240.

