#### 3 STUDY DESCRIPTION

# 3.1 Background

Urolithiasis (kidney stones) affects 1 in 11 people in the United States and pain caused by urolithiasis is a common cause for presentation to the ED in the United States, totaling more than 1 million visits per year. Additionally, up to one in ten patients who present to the ED for kidney stones return to the ED for reevaluation and as many as a third of these patients require admission to the hospital.8 While complications of kidney stones may necessitate treatment with antibiotics, procedural interventions and admission to the hospital, the vast majority of both the initial and repeat ED visits are due to uncontrolled pain but are unlikely to result in procedural intervention. Often, uncontrolled pain may be accompanied with nausea which limits the ability of patients to utilize oral medications both in the ED and at home leading to the frequent need for parenteral medications, commonly opioids and non-steroidal anti-inflammatory medications, to break the cycle of severe pain caused by kidney stones. At U-M, our preliminary data (Appendix Table 1) demonstrates that approximately 50% of patients receive 2 or more doses of parenteral medications to treat kidney stone related pain in the ED. Nationally, diagnosis of kidney stones has been associated with long term opioid use and opioid medications are often prescribed after ED visits related to kidney stones. 10,11 Recent efforts to reduce opioid use and prescribing in the ED has led clinicians to seek alternative therapies to treat severe and refractory pain including the use of regional anesthesia. 1,2

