#### 3.6 Outcomes

#### 3.6.1 Primary Outcome and rationale

The primary outcome will be the proportion of patients receiving a second parenteral pain medication in the ED after a single-shot ESPB is performed by a study investigator. We have reviewed historical data that suggests that the rate of response (percentage of patients that do not require a second parenteral pain medication) in patients with urolithiasis, and who receive a parenteral medication as the first analgesic in the ED (approximately 70% of all kidney stone patients), ranges from 47 to 57% for the years 2020 – 2022. The average response rate is 53.4% during this period which is in line with historical trends prior to the Covid-19 pandemic.

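### Section 4.4 admits controls on any parenteral medication, while ESPB patients and the 53.4% baseline need a parenteral pain medication; any matched control without one biases the primary comparison toward no difference.

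*Combined protocol and SAP*

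**What the plan says.** Control eligibility is defined only in section 4.4. Its medication criterion is that the patient "received at least one dose of parenteral medication while in the ED". The criterion for ESPB patients in section 4.2, repeated in 2.6, is "Patient received one dose of parenteral pain medication in the ED".

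The primary outcome in section 3.6.1 is "the proportion of patients receiving a second parenteral pain medication in the ED after a single-shot ESPB is performed". A responder is a patient who does not receive one.

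The planning rate uses the narrower population. Section 2.10 reports "572 out of 1071 patients (53.4%) presenting to the ED and meeting the inclusion criteria" as not needing a second dose, and 3.6.1 describes the group as those "who receive a parenteral medication as the first analgesic in the ED".

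Section 7.2 matches controls 3:1 on a propensity score that includes the type of the first pain medication. It gives no levels for that variable, no exact matching and no caliper. Section 6.4 says control data come from an EHR query. No list of qualifying drugs appears in 4.4, 6.4 or 7.2.

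**The concern.** The control criterion is the only one of these definitions that does not restrict the drug to an analgesic. Taken at its word, it admits a stone patient who had an injected antiemetic and only oral analgesia, or none. That patient could not have entered the ESPB arm. With no first parenteral analgesic there is hardly room for a second, so the patient is a responder almost by definition.

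Such patients are plausible. Section 3.1 notes that "uncontrolled pain may be accompanied with nausea", and 3.6.1 implies that a minority do not receive a parenteral drug as their first analgesic.

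At stake is the primary analysis in 7.2, which is the comparison with these matched controls. Each such control raises the control response rate and narrows the measured difference. Section 7.4 uses the same controls for the ED operations and opioid comparisons, so the mismatch carries over there too, though the documents do not show in which direction.

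**Working it through.** **1. The plan's own figures.** 572/1071 = 0.534, as stated in 2.10. An exact binomial search for Simon's optimal design with response rates 0.55 and 0.75, α = 0.05 and β = 0.10 gives:

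- stage 1: stop at 10 or fewer responders of 18;
- final: more than 35 responders of 54 needed;
- exact α 0.0477, power 0.9007.

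This matches the 18 and 54 in 2.10. Since 18 − 10 = 8, it also matches the rule in 7.3 of stopping when 8 or more receive a second dose. None of these figures uses the controls, so none depends on the wording of 4.4.

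**2. Inputs for the comparison.**

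- Control baseline 0.55 and ESPB response 0.75 (2.10). The observed 0.534 is used as a sensitivity value.
- 60 ESPB patients and up to 180 controls (2.10).
- α = 0.05 (7.1). Sidedness is not stated; two-sided is assumed.
- x, the share of *matched* controls given only a non-analgesic injection. The documents give no value, so 0 to 20% is an assumption.
- All such controls are taken to be responders (assumption).

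**3. Formulas.** Control response: pc = 0.55 + (1 − 0.55)·x. Difference: d = 0.75 − pc. Each 10% in x therefore costs 0.45 × 10 = 4.5 points.

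Power (normal approximation) = Φ[(d − 1.96·SE0)/SE1], where

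- SE0 = √[p̄(1 − p̄)(1/60 + 1/180)], with p̄ = (60 × 0.75 + 180·pc)/240;
- SE1 = √[0.75 × 0.25/60 + pc(1 − pc)/180].

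The calculation ignores the matching and the interim stop.

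**4. Worked case, x = 0.** p̄ = (45 + 99)/240 = 0.60; SE0 = √(0.24 × 0.02222) = 0.0730; SE1 = √(0.003125 + 0.001375) = 0.0671. Then (0.20 − 0.1431)/0.0671 = 0.848, so power is 0.80.

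**5. Results.**

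| x | Control response | Difference (points) | Power | Power from 53.4% baseline |
|---|---|---|---|---|
| 0 | 55.0% | 20.0 | 0.80 | 0.86 |
| 5% | 57.3% | 17.8 | 0.70 | 0.77 |
| 10% | 59.5% | 15.5 | 0.58 | 0.66 |
| 20% | 64.0% | 11.0 | 0.34 | 0.41 |

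**6. What decides x.** Every ESPB patient has had a parenteral analgesic. If the first-analgesic variable has its own level for none or oral, no treated patient occupies that level. Controls in it then have an estimated propensity near zero and would hardly ever be matched. If the variable is left missing for them, they may be dropped. If it is coded by drug class without route, so that an oral anti-inflammatory shares a level with an injected one, they can be matched. The plan does not say which applies.

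**The case against.** The strongest reply is that the missing word is shorthand. Section 3.1, the rationale in 3.4, section 3.6.1 and the rationale under 4.2 all speak of parenteral medications without the qualifier and plainly mean analgesics. The nausea sentence in 3.1 goes on to say that nausea leads to parenteral opioids and anti-inflammatories, so it gives only weak support for patients who had an injected antiemetic and nothing else. The sponsor has also already applied the pain-medication filter once, to obtain the 1071 patients in 2.10. And the propensity score may exclude such controls without any change to 4.4.

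All of this makes the number of affected controls uncertain, and zero fits the documents. It does not close the gap. In the other sections the context supplies the meaning; 4.4 has no such context. No drug list, variable coding, exact matching or caliper is given that would settle it.

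A reader might infer more than the documents support:

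- **That the measured effect will shrink.** This needs such controls in the matched set, not merely in the pool.
- **That about 30% of controls are affected**, from 3.6.1's patients "who receive a parenteral medication as the first analgesic in the ED (approximately 70% of all kidney stone patients". The remainder are patients whose *first* analgesic was not parenteral. Some may have had one later, and nothing says how many had a non-analgesic injection.
- **That antibiotics are a common route in.** Controls must have uncomplicated stones, and 3.1 links antibiotics to complications.
- **That the comparison is conservative overall.** For ESPB patients only doses after the block count, whereas 4.4 sets no start point for a control's second dose. That pushes the other way, so the net direction is not established.

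**Conclusion.** The inconsistency is real and should be corrected. Section 4.4 as written admits controls who could not have entered the ESPB arm and who do not belong to the population behind the 53.4% baseline. Any of them who is matched biases the primary comparison toward no difference.

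The size is conditional. It rests on an undocumented x, on all such controls being responders, and on a two-sided test at 0.05. Across the assumed 5 to 20%, the loss is 2.3 to 9.0 points of a 20-point difference; at x = 0 there is no loss. These figures are an illustration, not an estimate for this trial. The point concerns this one component of bias and leaves the single-arm sizing of 18 and 54 and the futility rule intact.

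**What to change.** In section 4.4, make criterion 2 at least one dose of a parenteral *pain* medication. Define one list of qualifying parenteral analgesics and use it in the EHR query for eligibility and for the primary outcome, in both groups. Exclude controls without such a dose before matching. In section 7.2, state the levels of the first-analgesic variable, including whether route is part of the coding.

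The cost is a wording change and a query filter. The control pool becomes slightly smaller, and no new data are needed.

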#### 2.8 Primary outcome

Proportion of patients that receive a second parenteral medication for pain related to urolithiasis

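### The primary event is counted from the block in ESPB patients but from no defined time in controls, and no rule covers drugs given together, which favours ESPB under a dose count

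*Combined protocol and SAP*

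**What the plan says.** **ESPB arm.** Eligibility in 4.2 reads "Patient received one dose of parenteral pain medication in the ED". The primary outcome in 3.6.1 is the "proportion of patients receiving a second parenteral pain medication in the ED after a single-shot ESPB is performed by a study investigator", so drugs given before the block are outside the count.

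**Controls.** Section 4.4 requires that the patient "received at least one dose of parenteral medication while in the ED". Section 7.2 compares the outcome with 3:1 propensity-matched controls, with data from an EHR query. Neither section sets an index time for controls or a rule for drugs given at the same time. The propensity model includes the type of initial pain medication, but its coding is not described.

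**Outcome and historical data.** Section 2.8 gives the outcome as "Proportion of patients that receive a second parenteral medication for pain related to urolithiasis", with no starting point. Section 3.1 names opioids and non-steroidal drugs as the common parenteral agents and reports local data as a count of doses: "approximately 50% of patients receive 2 or more doses of parenteral medications to treat kidney stone related pain in the ED". Section 2.10 reports that "572 out of 1071 patients (53.4%) presenting to the ED and meeting the inclusion criteria did not require a" second parenteral pain medication, and sets the baseline response at 55%.

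**The concern.** Take a patient given a parenteral opioid and a parenteral non-steroidal drug together on arrival, with no further need. As a control this patient meets 4.4 and, if the query counts doses or drugs, has two and is a non-responder. In the ESPB arm the same treatment cannot produce an event. If the site takes 4.2 to mean exactly one dose, the patient is not enrolled. If the patient is enrolled, both drugs precede the block and 3.6.1 ignores them. Either way, initial combination treatment can be scored as rescue in controls only.

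The comparator's response would then be too low, and a block with no effect could look beneficial on the primary endpoint. If the query behind the 1071 historical patients counted in the same way, the baseline used for the two-stage design would also be too low.

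**Working it through.** **1. The plan's own figures.** 572/1071 = 53.4%, leaving 499 (46.6%) with a second medication. An exact search for Simon's optimal design with response rates 0.55 and 0.75, one-sided alpha 0.05 and beta 0.10 gives: stop at 10 or fewer responders of 18, then reject at more than 35 of 54. Exact alpha is 0.0477 and power 0.9007. This matches the stated 18 and 54. Ten or fewer responders of 18 is the stated rule of 8 or more with a second medication. The 35/54 cut-off comes from this search; the plan does not state it.

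**2. Inputs for the comparison.** 60 ESPB patients and 180 controls (2.10); observed control response 53.4% (2.10, 3.6.1); two-sided 0.05 (7.1). The share *c* of controls started on two co-administered parenteral analgesics is **not in the documents** and is assumed to be 0%, 5% or 10%.

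**3. Assumptions.** Every such control counts as a failure; matching removes none of them; the block adds nothing. Combination-start patients are either not enrolled in the ESPB arm or, if enrolled, have the same later need for rescue as other patients.

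**4. Formula.** If 53.4% is the observed response and a share *c* fails only through the counting, the response without the artefact is 0.534/(1 − *c*):

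- *c* = 5%: 0.534/0.95 = 56.2%, a gap of 2.8 points
- *c* = 10%: 0.534/0.90 = 59.3%, a gap of 5.9 points

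The ESPB arm would show this rate with no block effect, while the controls show 53.4%.

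**5. Chance of a significant result favouring ESPB.** Sum the products of the binomial (60) and binomial (180) probabilities over all outcomes with pooled z > 1.96:

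| *c* | ESPB response, no effect | Control response | Chance of a result favouring ESPB |
|---|---|---|---|
| 0% | 53.4% | 53.4% | 2.4% |
| 5% | 56.2% | 53.4% | 5.5% |
| 10% | 59.3% | 53.4% | 12.0% |

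**6. The two-stage design, only if the historical query counted co-administered drugs separately.** With a block that adds nothing, the 10/18, 35/54 rule rejects the 55% null with probability 6.8% at 56.2% response and 14.9% at 59.3%. The corresponding figures are 4.8% at 55% and 2.9% at 53.4%. Because 53.4% was rounded up to 55%, the null itself would be low by 56.2 − 55 = 1.2 or 59.3 − 55 = 4.3 points.

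**The case against.** Four objections carry weight.

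**The eligibility wording.** A reader might infer that the contrast between one dose in 4.2 and at least one in 4.4 causes the bias. The documents do not support this. Controls are observed over a completed ED stay, and limiting them to exactly one dose would make every control a responder. Section 2.10 also uses one dose as a threshold: 499 of the 1071 patients said to meet the inclusion criteria had a second medication.

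**No stated counting rule.** A reader might infer that controls given two drugs together are failures by rule. No section says so. Sections 2.10 and 3.6.1 speak of not requiring a second medication, and 6.4 allows chart review to confirm EHR data. Appendix Table 1, cited in 3.1, is not in the text available and might clarify the count. The failure follows from a dose count, which 3.1 suggests but does not establish for the primary endpoint.

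**The null.** A reader might infer that the control criterion lowers the 55%. That figure comes from a different cohort, the 30 months to May 2022, and was rounded up from 53.4%. It is affected only if that query also counted co-administered drugs separately.

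**Matching.** If combinations have their own level of initial medication type and few ESPB patients started on them, matching would remove many of the affected controls. This stands as mitigation, but the coding is not given. Where combination-start patients are enrolled, matching would pair them with controls who all fail under a dose count, so the event definition still has to change.

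The four objections limit how far the point reaches. None of them supplies the missing control index time or the rule for drugs given together.

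**Conclusion.** The point holds as a difference in how the primary event is ascertained. The ESPB arm has a starting point and controls have none, and the plan does not say how drugs given together are counted. Under a dose count the direction is clear: it favours ESPB.

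The size is conditional. Under the assumptions listed above, a share of 5% roughly doubles the chance of a false result favouring ESPB and a share of 10% raises it about fivefold (12.0/2.4). At a share of zero there is no distortion from co-administration. Larger shares would be worse but have no support in the documents: 20% would need 0.20 × 1071/499 = 43% of the historical failures to be artefact, and 30% would need 64%. The documents do not establish that the 55% null is wrong, only that it should be recounted.

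**What to change.** - **Sections 4.4 and 7.2:** define the event identically in both arms. Parenteral analgesics given together as initial treatment count as one initial treatment; only a later administration is the event, over a prespecified interval.
- **Control index time:** give controls a starting point comparable to the time of the block. Grouping the initial drugs alone would leave controls counted from soon after the first drug and ESPB patients only from the block.
- **Propensity model:** code initial combinations as their own level of initial medication type.
- **Sections 4.2 and 4.4:** align the wording on qualifying analgesia with the shared definition.
- **Baseline:** recount 572/1071 under this definition before the interim. If it changes, restate the null and the design's operating characteristics.

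The cost is a few definitions and a rerun of the existing EHR query, which would also show the true share started on two drugs. The downside is that the baseline response may rise, making the stated effect size less favourable.
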